4.1 OVERALL DESIGN

The aim of this study is to conduct a randomized pilot trial of the refined OA-PCP among n=240 patients with knee and / or hip OA. Sub-aims and hypotheses are:

1. Obtain data on the efficacy of the OA-PCP.
H₁ Participants in OA-PCP intervention will have greater improvement in objectively assessed PA, measured at 6 and 12 months, compared to participants in an attention control group.
H₂ Participants in OA-PCP intervention will have greater improvement in self-reported physical function and pain, measured at 6 and 12 months, compared to participants in an attention control group.
2. Refine the OA-PCP based on feedback from patients, clinic personnel, and community representatives, in preparation for a larger, implementation-focused trial.

This study will be a randomized trial with participants assigned equally to either the OA-PCP or an attention control group (Figure 2). To enhance generalizability, we will involve patients broadly from UNC Health Care and affiliated clinics within the UNC Physicians Network as well as Piedmont Health Services. Randomization will be based on a computer generated sequence maintained by the project statistician in a database. Participants will be notified of their randomization assignment by the study coordinator, following completion of baseline assessments. Study patients will complete assessments at baseline, 6 months and 12 months. The 12-month time point corresponds to the end of OA-PCP follow-up calls (described below), and the 6-month time point allows assessment of the time course of changes.

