5.5 STRATEGIES FOR RECRUITMENT AND RETENTION

Potential participants will first be identified using the electronic medical record (EMR). Specifically, we will identify patients age 65 and older with diagnosis codes for knee or hip OA (M17.0, M17.10, M17.11, M17.12, M17.2, M17.30, M17.31, M17.32, M17.4, M17.5, M17.9, M16.0, M16.10, M16.11, M16.12, M16.2, M16.30, M16.31, M16.32, M16.4, M16.50, M16.51, M16.52, M16.6, M16.7, M16.9, M19.90, M19.91, M19.92, M19.93, M15.0 (primary, generalized OA)), a diagnosis code for at least one qualifying comorbid health condition under CCM guidelines listed above, and no diagnosis codes for exclusionary health conditions. We will include patients who have been seen within UNC by a primary care provider during the past 2 years, including Internal Medicine, Family Medicine and Geriatrics clinics. Primary care providers may, if they choose, review lists of patients eligible based on the EMR and approve a final list of patients to contact, but this is not a requirement. These patients will be mailed an introductory letter and then called by a study team to further assess eligibility. Patients who are eligible and interested in participating will complete a verbal consent process which will include verbal HIPAA authorization. Then participants will complete baseline assessments via telephone and be mailed an accelerometer for physical activity assessment. Participants will be paid \$25 for completing each phone-based assessment and \$15 for returning the accelerometer at each time point. Following return of the accelerometer at baseline, an unblinded study team member will call the participant to inform them of their randomization assignment. Participants assigned to the OA-PCP group will then be mailed an Activity Tracker and instructions and asked to begin wearing it as soon as they receive it. About a week after the Activity Tracker is mailed, an unblinded study team member will call the participant to answer any questions about device wear and setup. We will aim for the participant to wear the Activity Tracker for at least 1 week prior to the first OA-PCP call, so that PA goals can be based on current activity patterns. Participants will also be notified that the PA Coach will be able to view their Activity Tracker data using Fitabase®.

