6.3 MEASURES TO MINIMIZE BIAS: RANDOMIZATION AND BLINDING

The randomization scheme will be generated by the study statistician and stored within the study database. The database will be configured so that blinded study personnel (e.g., those conducting follow-up assessments) will not have access to randomization information. The participants will not be notified of randomization assignment until all baseline assessments are complete. In addition, an individual participant's randomization assignment will not be known to any study personnel until baseline assessments are complete. Randomization will be stratified according by clinic site.

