minimal loss of monitors (< 2%). In Aim 2 of this project, valid accelerometer data were available for 57 participants at baseline (95%) and 52 participants at follow-up (86%). Upon return, accelerometer data will be downloaded, compiled into 60s epochs, processed to identify wear, non-wear, and sleep periods using current algorithms^{89,90}, and summarized using cut-points developed by Troiano⁸⁹ and Mathews⁹¹. These cut-points will allow us to calculate minutes of MVPA, as well as sedentary time and step counts.

Secondary Efficacy Outcomes:

Self-Reported Physical Function. Physical function is a key outcome in OA and can be improved with regular PA^{14,15}. We will assess physical function with the widely used Western Ontario and McMaster Universities Osteoarthritis Index (WOMAC) subscale^{92,93}; it includes 17 items, rated on a Likert scale of 0 (no difficulty) to 4 (extreme difficulty), that assess difficulty with performing a range of daily activities commonly affected by lower extremity OA. The reliability and validity of the WOMAC total score and subscales have been confirmed⁹³. In patients with hip or knee OA, Bellamy et al. reported internal consistency coefficients (Cronbach's alpha) between 0.86 and 0.95 on WOMAC subscales.

Pain (WOMAC). We will assess self-reported pain using the WOMAC subscale^{14,15}; it includes 5 items, rated on a Likert scale of 0 (no pain) to 4 (extreme pain), that assess pain during a range of daily activities.

Exploratory Outcomes:

Stanford Numeric Rating Scale (NRS) for Fatigue: We will assess self-reported fatigue using the Stanford NRS Scale for Fatigue; it includes 1 item, rated on a Likert scale of 0 (no fatigue) to 10 (severe fatigue), that assesses fatigue in the past 2 weeks.

Self-reported Physical Activity: Modified version of the CHAMPS (Community Health Activities Model Program for Seniors) Physical Activity Measure⁹⁴. This measure complements the accelerometer-based data by providing additional information on the contexts and types of activities in which participants are engaging. This modified version of the CHAMPS includes items tailored for this participant group. For each item, participants first indicate whether they have done the activity for 10 or more minutes during the past week. If they respond "yes," they will be asked the number of days and minutes per week. This questionnaire will be supplemented with individual items to assess sitting behavior and sleep.

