9.2 SAMPLE SIZE DETERMINATION

We note that this study is an extended exploratory phase, in which we are interested in obtaining estimates of efficacy that will inform a larger trial that is adequately powered to detect clinically meaningful differences in MVPA. Our sample size was selected on the basis of feasibility for this exploratory study and involvement of a sufficient number participants to adequately assess intervention and study procedures. We provide here a description of expected statistical power for this sample size. Based on previous research on PA

interventions for OA^{98,99}, we expect an effect

size of 0.3-0.7, though have examined a range of possible values from 0.2-0.8 (Table 2). We also account for 10% attrition, based on our prior work. A sample size of 240 participants (120 per group) will provide approximately 80% power at 5% level of significance to detect a small-to-medium effect size of 0.38 or greater for the difference in minutes of MVPA between intervention and control groups, accounting for expected attrition.

$\alpha=0.05$	Power=80%	Power=85%	Power=90%	Power=95%
Effect size	Sample size	Sample size	Sample size	Sample size
0.20	787	900	1053	1301
0.30	351	401	469	579
0.40	198	226	265	327
0.50	128	146	170	210
0.60	90	102	120	148
0.70	68	76	88	110
0.80	52	60	68	84

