9.4 STATISTICAL ANALYSES PLAN

Preliminary analyses will include generating descriptive statistics for demographic variables, as well as baseline characteristics and follow-up measures. This includes means and standard deviations for continuous variables, and frequencies and percentages for categorical variables. Ranges will also be examined for outliers and to ensure data integrity. Demographics and baseline characteristics will also be described separately by randomized group.

We hypothesize that participants receiving the OA-PCP will have greater improvement in MVPA compared with the attention control group at 6 and 12 months. To determine the effects of the intervention on MVPA, repeated measures will be analyzed using linear mixed effects models, with clinic included as a random effect, to estimate mean change and 95% confidence intervals in MVPA from baseline to 6-month and 12-month time points. This model will account for intra-person clustering for the repeated measures, including a group x time effect. We will use the same modeling strategy for continuous secondary and exploratory outcomes. An advantage of this modeling approach is that it uses all available data; participants are not dropped if they miss a time point. This approach will reduce the overall amount of missing data and could eliminate the need for imputation of missing repeated outcomes¹⁰⁰. However, if we find that missing data are related to measured patient factors (i.e., missing not at random [MNAR]), we will carry out sensitivity analyses by imputing missing values under the MNAR scenario and examining the results. The SAS procedure PROC MI has several options for using multiple imputation in sensitivity analyses based on pattern-mixture models for MNAR data, which model the distribution of a response as the mixture of a distribution of the observed responses and a distribution of the missing responses¹⁰¹. Multiple imputation has the advantage of providing a framework for incorporating information from these variables, while preserving a parsimonious main treatment effect model^{102, 103}. Analyses will be conducted on an intent-to-treat basis and carried out using SAS 9.4 (SAS Institute Inc., Cary, NC). Tests will be two-sided and considered significant at the 0.05 level.

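### Section 9.4 names neither baseline adjustment nor a common baseline mean for MVPA, leaving an optional gain in precision unspecified

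*Combined protocol and SAP*

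**What the plan says.** Section 9.4 is the only description of the primary model. It is a linear mixed model on the repeated measures, with clinic as a random effect, used "to estimate mean change and 95% confidence intervals in MVPA from baseline to 6-month and 12-month time points". On structure it adds: "This model will account for intra-person clustering for the repeated measures, including a group x time effect". The fixed effects are not listed. Neither this section nor any other names baseline MVPA as a covariate or sets the two arms to a common baseline mean. The approach carries over to other endpoints: "We will use the same modeling strategy for continuous secondary and exploratory outcomes".

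Three sections govern the timing of disclosure. Section 4.1: "Participants will be notified of their randomization assignment by the study coordinator, following completion of baseline assessments". Section 6.3 says that an individual's "randomization assignment will not be known to any study personnel until baseline assessments are complete". Section 5.5 ties this to the accelerometer itself: "Following return of the accelerometer at baseline, an unblinded study team member will call the participant to inform them of their randomization assignment".

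Section 9.2 describes the purpose of this exploratory phase as "obtaining estimates of efficacy that will inform a larger trial".

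**The concern.** Change is estimated from baseline, so baseline is evidently one of the modelled responses. Coded in the usual way, the model estimates a separate baseline mean in each arm. The treatment effect is then the follow-up difference minus the observed baseline difference, apart from the adjustment for missing values. Because assignment is withheld until baseline data are in, the true baseline difference is zero. Estimating it freely and subtracting it adds noise to the contrast.

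This concerns efficiency, not validity. Efficiency matters here because the main product is an efficacy estimate with its interval, for use in planning a larger trial. Section 9.2 says the sample size was set by feasibility, so the analysis is the cheapest place left to gain precision. The same model serves WOMAC pain and function. Naming the fit in advance also avoids choosing between the two versions after the baseline imbalance has been seen.

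**Working it through.** **Inputs from the documents.** 240 participants, 120 per arm, 10% attrition, effect size 0.38, two-sided 5% level (sections 9.2 and 9.4); measurements at baseline, 6 and 12 months (section 4.1); valid accelerometer data in Aim 2 from 57 participants at baseline (95%) and 52 at follow-up (86%) (section 8.1).

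**Assumed, because the documents do not give them.** The correlation rho between time points, and the ratio r of baseline SD to follow-up SD. The follow-up SD is set to 1. The clinic effect is left out.

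**The plan's own figure.** With 120 x 0.9 = 108 per arm, power = Φ(0.38/√(2/108) − 1.96) = Φ(0.83) = 79.7%. The stated figure of about 80% is reproduced. Section 9.2 does not say which SD the 0.38 refers to, so this figure cannot decide between the two fits.

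**Variance of the treatment contrast.** With n = 120 per arm and a proportion m of follow-up missing completely at random, for baseline and one follow-up:

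- common baseline mean: 2(1 − rho²)/(n(1 − m))
- separate baseline means: the same, plus 2(r − rho)²/n

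With r = 1 and m = 0.10:

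| rho | Common baseline | Separate baselines | Avoidable share |
|---|---|---|---|
| 0.3 | 2(0.91)/108 = 0.01685 | + 2(0.49)/120 = 0.02502 | 32.6% |
| 0.5 | 2(0.75)/108 = 0.01389 | + 2(0.25)/120 = 0.01806 | 23.1% |
| 0.7 | 2(0.51)/108 = 0.00944 | + 2(0.09)/120 = 0.01094 | 13.7% |

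The share is 1 − common/separate, so its base is the variance of the usual fit. As inflation over the common-baseline fit, the same figures are 48.5%, 30.0% and 15.9%.

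**All three occasions.** Generalised least squares with equal correlation between time points and independent 10% missingness at 6 and 12 months gives these avoidable shares (%), identical at both times:

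| r | rho 0.2 | 0.3 | 0.5 | 0.7 | 0.9 |
|---|---|---|---|---|---|
| 0.5 | 7.8 | 3.8 | 0 | 6.7 | 43.6 |
| 0.7 | 19.0 | 13.7 | 4.6 | 0 | 16.2 |
| 0.85 | 28.4 | 23.1 | 12.9 | 3.9 | 1.2 |
| 1 | 37.6 | 32.7 | 23.3 | 13.9 | 4.6 |
| 1.2 | 48.4 | 44.6 | 37.3 | 30.9 | 30.3 |

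The gain vanishes when r = rho. At r = 1 and rho 0.3/0.5/0.7:

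- complete data, (1 − rho)/2: 35/25/15%
- Aim 2 valid-wear rates (5% missing at baseline, 14% at follow-up): 33.5/24.2/14.7%
- 95% interval narrower by 1 − √(1 − share): 18.0/12.4/7.2%
- participants the usual fit would need to match 240 under the common-baseline fit, 240/(1 − share): 357/313/279

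**Simulation.** In 8,000 two-occasion trials per setting with a true effect of 0.38 and r = 1, both estimators averaged 0.378 to 0.379. The variance reduction was 33.8% at rho 0.3 and 12.6% at rho 0.7. A separate check of the finite-sample cost (108 per arm, estimated covariance, baseline-adjusted against change-score estimate) found a loss of 0.5% of the variance at r = rho = 0.7 and 0.2% at r = rho = 0.5.

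**The case against.** The strongest reply is that no error has been shown. The plan's contrast is valid, its wording does not exclude a common-baseline fit, and the percentages belong to the customary coding, which the text does not spell out. This is right, and it is why the point is optional.

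A second objection is that the 14–33% range depends on equal SDs, which nothing in the documents supports. Section 5.1 admits only people who report under 150 minutes of activity per week. That may restrict the baseline spread and push r below 1, where for these correlations the gain is smaller: 23/13/4% at r = 0.85 and 14/5/0% at r = 0.7. Selection is on self-report rather than on the accelerometer, so the size of this effect is unknown. The caution stands, and the equivalent sample sizes should be read as illustrations.

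Third, the claim that nothing is lost depends on the covariance model. Section 9.4 does not name a within-person covariance, and a random intercept would satisfy its wording. Under a compound-symmetric working covariance with 10% missing, the common-baseline constraint increases the variance by about 9% at r = rho = 0.7 and at r = rho = 0.5, and by about 18% at r = 0.5, rho = 0.7. This is correct. The unstructured covariance is therefore an essential part of the proposal.

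Fourth, the finite-sample check used two occasions, with no clinic effect. It indicates the likely cost and does not test the full model.

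**Conclusion.** The point holds as an optional improvement in precision. The plan neither specifies nor excludes a common baseline mean, and the timing of assignment justifies one. Under the customary coding, about 14–33% of the variance of the contrast is avoidable if SDs are equal, 10% of follow-up is missing and rho lies between 0.7 and 0.3. Over the wider grid the share runs from 0 to 48%. Every figure except the missingness rates rests on assumed SDs and correlations. With an unstructured covariance the constrained fit is, in large samples, never less precise; at about this sample size the simulated worst-case loss is about 0.5% of the variance. There is no bias, no wrong analysis and no demonstrated shortfall against the stated 80% power.

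**What to change.** In section 9.4, list the fixed effects and specify a constrained longitudinal model:

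- baseline, 6-month and 12-month values as responses;
- time plus group x post-baseline time, with no group main effect, so that both arms share one baseline mean;
- an unstructured within-person covariance, stated explicitly;
- clinic as already planned.

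Report the group differences in change at 6 and 12 months, and use the same model for WOMAC pain and function. Mean change from baseline and the use of all available data are both kept. If this is already the intended fit, one sentence saying so is enough.

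The cost is about a sentence of text, a small change to the fixed-effects statement in SAS and naming the covariance structure. No new data are needed. The gain may be close to nil if the baseline SD turns out to be about rho times the follow-up SD.

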We selected this as the primary study outcome because PA is the target of the intervention, and objective assessment has advantages over self-report in terms of accuracy⁸⁶. Our specific primary outcome of interest is minutes of moderate to vigorous intensity PA (MVPA) per week, since this corresponds to DHHS recommendations and is a known predictor of outcomes in patients with OA⁷⁸. We will also examine step counts, minutes of sedentary activity and other complementary metrics, as these are also important for providing a broad picture of PA among participants^{80,87}. Each participant will be asked to wear the Actigraph GT3X+ (Pensacola, FL), which allows for the collection and manipulation of raw actigraphy data to facilitate accurate assessment of PA⁸⁸. Participants will be asked to wear the monitors during all waking hours for 7 days. Following previously established thresholds, outcomes will only be computed for participants who wear the accelerometer for 4+ days with 10+ hours of daytime wear. Monitors will be worn on the waist, using either an elastic belt or clip, over the right hip. We may ask a subset of participants to wear a wrist-worn monitor in addition to the waist-worn monitor, in order to assess acceptability and compare values obtained from monitors worn at the two different sites. Accelerometers will be mailed with instructions and a pre-stamped / addressed return envelope. Several days after the accelerometer has been mailed, a study team member will call the participant to review instructions. A phone number will be provided for problems or questions. A second call will be made toward the end of the 7 days to ask about wear and to remind participants to return the monitor. If participants have not worn the monitor enough, they will be asked to wear the monitor a few extra days. Drs. [name], [name] and [name] have been involved with projects that have successfully mailed accelerometers to and / or from study participants with OA. There have been high rates of adherence (4+ days with 10+ hours of wear); 93% in one study of adults and partners with OA and 89% in another of 140 patients with OA, with

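### Section 9.4 defines missingness related to measured factors as MNAR and makes it the trigger for the only missing-data sensitivity analysis, but that trigger cannot tell MAR from MNAR

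*Combined protocol and SAP*

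**What the plan says.** Section 9.4 fits a linear mixed model with a group-by-time effect and a random clinic effect to all available MVPA data. It says this approach "could eliminate the need for imputation of missing repeated outcomes". One conditional commitment follows: "if we find that missing data are related to measured patient factors (i.e., missing not at random [MNAR]), we will carry out sensitivity analyses", to be done "by imputing missing values under the MNAR scenario and examining the results". For the tool, it notes that PROC MI "has several options for using multiple imputation in sensitivity analyses based on pattern-mixture models for MNAR data", but it selects no option, delta, pattern restriction or reference arm. It then credits multiple imputation with providing a "framework for incorporating information from these variables, while preserving a parsimonious main treatment effect model".

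No other missing-data sensitivity analysis appears. The supportive analyses in Section 9.3 concern how much of the intervention participants completed, not missing outcomes. Under Section 8.1, MVPA is not computed for anyone with fewer than 4 days of at least 10 hours' wear, so the primary outcome can be missing even for a participant who stays in the study.

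**The concern.** The parenthesis equates two different mechanisms. If missingness depends only on measured factors, the data are MAR given those factors. They are MNAR if, after conditioning on everything observed, missingness still depends on the value that was not seen. An association between missingness and measured factors can arise under either mechanism, and it can be absent under MNAR.

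The error matters because it controls an action. Followed literally, the rule can omit the MNAR analysis when it is needed, because no measured factor happens to predict missingness. It can also call for an MNAR analysis when a MAR imputation using those factors would do. The later sentence on bringing these variables into the imputation describes that MAR remedy, yet the only analysis committed to is one under MNAR.

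Section 9.2 says the trial is meant to supply efficacy estimates for a larger trial. Readers of those estimates need to know how far they rest on MAR, and the rule can leave that unexamined.

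**Working it through.** **1. Definitions.** Let R indicate a missing follow-up value, Y the follow-up MVPA and X the measured factors.

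- MAR: P(R | X, Y_obs, Y_mis) = P(R | X, Y_obs).
- MNAR: the left side still varies with Y_mis.
- The trigger looks only at whether R is associated with X. That association is expected under MAR through X. It also appears under MNAR if X correlates with Y_mis, and it is absent under MNAR if missingness follows the part of Y that X does not predict.

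**2. Scale.** Section 9.2 states about 80% power for an effect of 0.38 SD with 120 per group and 10% attrition. With 120 × 0.9 = 108 per arm, power is Φ(0.38 × √(108/2) − 1.96) = Φ(0.83) = 79.7% (79.4% by the t-test). The stated figure is reproduced, so 0.38 SD is the yardstick below.

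**3. How often the trigger fires, one factor.** The plan names no factor, test or threshold, so these settings are assumptions: 120 per arm; X ~ N(0,1); Y = rX + e + 0.38 × group; logistic missingness with odds 2 or 3 times higher per SD lower; 10% or 13.3% missing; trigger is p<0.05 for X by missing status; 3,000 trials per cell. The same mechanism acts in both arms.

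| Mechanism | Trigger fires | Bias of X-adjusted effect |
|---|---|---|
| MCAR | 4–6% | – |
| MAR, through X | 86–100% | within 0.004 SD |
| MNAR, through Y, r = 0 | 5% | −0.006 to −0.040 SD across all r |
| MNAR, through Y, r = 0.3 | 16–32% | as above |
| MNAR, through Y, r = 0.5 | 34–71% | as above |
| MNAR, through Y, r = 0.7 | 58–95% | as above |
| MNAR, through e only | 4–6% | about 0 |

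**4. MNAR in the intervention arm only, two factors.** Assumptions: r = 0.6; log-odds slope of −1 per SD; two baseline factors, either significant at 5%; 2,000 trials per cell; a baseline-adjusted available-case regression in place of the mixed model. The expected false-positive rate is 1 − 0.95² = 9.75%.

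| Overall missing | MAR: fires | MAR: bias | MNAR, intervention arm: fires | MNAR: bias |
|---|---|---|---|---|
| 10% | 98.8% | +0.003 | 9.7% | +0.08 SD |
| 14% | 99.8% | −0.001 | 9.5% | +0.11 SD |
| 20% (upper case) | 99.95% | 0.000 | 9.8% | +0.15 SD |

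In these scenarios the trigger fires where the adjusted estimate is unbiased, and stays at its false-positive rate where it is biased.

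**5. Simple arithmetic for the same risk.** If non-responders in one arm are less active by delta than MAR predicts, bias = missing fraction × delta. The fractions are:

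- 10% from Section 9.2.
- 8/60 = 13.3%, from the 60 pilot participants (Section 2.1) and the 52 with valid follow-up data (Section 8.1).
- 5/57 = 8.8%, which assumes that the 3 pilot participants without valid baseline data are among those 8.

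| Missing in that arm | delta 0.25 SD | 0.5 SD | 0.8 SD |
|---|---|---|---|
| 8.8% | 0.022 | 0.044 | 0.070 |
| 10% | 0.025 | 0.050 | 0.080 |
| 13.3% | 0.033 | 0.067 | 0.107 |

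The deltas are assumptions; the documents give none. Equal missingness and equal deltas in both arms cancel.

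**The case against.** The strongest defence has five parts.

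- **Material bias needs a difference between arms.** Under the shared mechanisms bias is at most 0.04 SD, and it is about 0 in the shared case where the trigger fires least. The attention control is matched on dose and contact (Section 6.1), and the documents give no sign of differential loss. This stands as a limit on size. Equality cannot be assumed, though: only the OA-PCP arm receives a tracker, activity goals and coach review of activity data. Even there, one-arm bias of 0.05–0.13 SD is about 0.5 to 1.1 simulated standard errors of the group difference.
- **More factors would be tested.** Section 8.1 lists about ten participant characteristics. With ten independent factors, firing under shared MNAR in Y rises to 60–97% at r = 0.5–0.7. But ten unrelated factors also fire in 1 − 0.95¹⁰ = 40% of trials under MCAR. With five factors, one-arm MNAR fires in 21–25%, close to the chance rate 1 − 0.95⁵ = 23%. More testing raises firing everywhere without making it diagnostic.
- **Over-checking is harmless.** Running the analysis under MAR costs one table and leaves the primary estimate unchanged. True, so the harm lies in omission.
- **A charitable reading exists.** The model names only group, time and clinic, so missingness tied to other factors may be non-ignorable for that model. The authors may have meant this. The remedy would still be a MAR imputation with auxiliary variables, and the trigger would still not detect MNAR. The rule says if, not only if, so it forbids nothing, but it commits to nothing otherwise.
- **The trial is exploratory and the pilot evidence thin.** Both are fair. The pilot's follow-up interval and reasons for loss are not given. Reminder calls, extra wear days ("If participants have not worn the monitor enough, they will be asked to wear the monitor a few extra days") and payment for returning the device should limit loss, but they do not show that what remains is MAR.

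**Conclusion.** The point holds. The definition is wrong as written, and it governs the plan's only missing-data sensitivity analysis. The error lies in the robustness check: the wording creates no bias, and the mixed model remains valid under MAR given the variables in it.

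What could go unexamined is about 0.02 to 0.11 SD (6% to 28% of the 0.38 design effect: 0.022/0.38 and 0.107/0.38), if departures of 0.25 to 0.8 SD occur in one arm only. It is near zero if both arms depart equally. The firing rates depend on the assumed mechanisms, correlations and test. The conclusion that firing does not separate MAR from MNAR follows from the definitions and does not depend on those settings. This should be fixed, but it does not threaten the primary analysis.

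**What to change.** 1. Correct the definition in Section 9.4: missingness related to measured factors is MAR given those factors; MNAR is dependence on the unobserved value after conditioning on the observed data, and it cannot be tested.
2. If measured baseline factors predict missing MVPA, include them as auxiliary variables in a MAR multiple imputation, as the section's own sentence on these variables suggests. Leave the primary mixed model unchanged.
3. Whatever that check shows, run a prespecified delta-adjusted pattern-mixture (tipping-point) analysis of MVPA at 6 and 12 months. Use arm-specific deltas over a range fixed in advance, for example 0 to −0.8 SD in each arm, including equal deltas. The range and the choice of this method over reference-based imputation are for the study team, but both should be settled before unblinded data are seen.

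The cost is revised SAP wording and one extra programmed analysis in PROC MI, which the plan already names. It needs no new data and adds no participant burden. The downside is one more set of results to report.
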